- c 718-CIH-301 v2 Completers will resume IP at their Next Scheduled Study Treatment Visit (see [Table 8](#)). The Next Scheduled Study Treatment Visit may be any visit within the Treatment Period and will depend on the participant’s visit schedule, which will remain relative to the date of their Day 1 visit.
- d Both participants and study partners (if applicable) will be re-consented at the Re-Qualification Visit. A legally authorized representative may consent on behalf of participants who are not capable of providing informed consent in the opinion of the investigator.
- e Guidance on eligibility for 718-CIH-301 v2 Completers is provided in the Protocol (Section 7.1.3.1).
- f Any new or worsening conditions or events with an onset after the end of participation under 718-CIH-301 Protocol Version 2 (Day 395) and before informed consent for 718-CIH-301 Protocol Version 3 or higher will be recorded as Interim Medical History in the eCRF.
- g Participants and study partners (if applicable) will be re-trained, if need be based on participant’s comfort level, by study staff on the use of software applications, devices, and diaries necessary for the conduct of the study.
- h Vital signs include body temperature, respiratory rate, heart rate, and blood pressure. Blood pressure and heart rate will be measured after the participant has been in the supine position for at least 5 minutes and then repeated approximately 1 and 3 minutes after standing at all scheduled time points. Vital signs can be repeated once if out of range. At the Post Re-Qualification Safety Check-in, vital signs will be measured prior to dosing.
- i A full physical and neurological examination is to be conducted during the Re-Qualification Visit. At the Post Re-Qualification Safety Check-in, physical examinations will include a brief assessment of general appearance, cardiovascular, respiratory, gastrointestinal, and neurological systems and followed by a targeted physical assessment as needed. A symptom-directed examination may be conducted at any time at the discretion of the investigator.
- j To include hepatitis B and C screening tests, HIV-1 and HIV-2 antibody.
- k A single ECG will be measured after the participant has been in the supine position for at least 5 minutes.
- l Safety laboratory assessments will include blood samples for hematology, biochemistry, coagulation, and urine samples for urinalysis. At the Post Re-Qualification Safety Check-in, samples will be collected \leq 2 hours prior to dosing.
- m Serum pregnancy tests will be conducted for all female participants at the Re-Qualification Visit.
- n At the Post Re-Qualification Safety Check-in, participants will self-administer IP in the clinic under the supervision of study staff. All scheduled safety assessments will be conducted prior to dosing.
- o AEs/SAEs will be collected from the time of informed consent for 718-CIH-301 Protocol Version 3 or higher through end of study participation.
- p All medications, supplements, procedures, and therapies taken after the completion of Day 395 under 718-CIH-301 Protocol Version 2 will be recorded through the end of the study.

Table 8: Schedule of Assessments: Month 15 to Month 48 – All Participants

Assessments	Treatment Period ^a												Safety Follow-Up
	M 15 (±14 d)	M 18 (±14 d)	M 21 (±14 d)	M 24 (±14 d)	M 27 (remote) (±14 d)	M 30 (±14 d)	M 33 (remote) (±14 d)	M 36 (±14 d)	M 39 (remote) (±14 d)	M 42 (±14 d)	M 45 (remote) (±14 d)	M 48 or ET ^b (±14 d)	
Body weight				X				X				X	X
Vital signs (including orthostatics) ^c	X	X	X	X		X		X		X		X	X
Brief physical examination ^d	X	X	X	X		X		X		X		X	X
12-lead ECG ^e		X		X		X		X		X		X	
Safety laboratory assessments ^f	X	X	X	X		X		X		X		X	
Urine drug test		X		X				X				X	
Alcohol breath test		X		X				X				X	
Cigarette/tobacco use assessment				X				X				X	
Pregnancy test ^g	X	X	X	X	X	X	X	X	X	X	X	X	X
C-SSRS (Since Last Visit)	X	X	X	X	X	X	X	X	X	X	X	X	X
UHDRSj													

Assessments	Treatment Period ^a													Safety Follow-Up
	M 15 (±14 d)	M 18 (±14 d)	M 21 (±14 d)	M 24 (±14 d)	M 27 (remote) (±14 d)	M 30 (±14 d)	M 33 (remote) (±14 d)	M 36 (±14 d)	M 39 (remote) (±14 d)	M 42 (±14 d)	M 45 (remote) (±14 d)	M 48 or ET ^b (±14 d)		
IP accountability/return ^p	X	X	X	X		X		X		X		X		
IP dispensation ^q	X	X	X	X	X	X	X	X	X	X	X			
IP self-administration ^r						X (once daily in the morning)								
IP adherence monitoring ^s						X								
AEs/SAEs						X								
Prior and concomitant medications and procedures/therapies						X								

Abbreviations: AE = adverse event; AI = Apathy Inventory;

; C-SSRS = Columbia–Suicide Severity Rating Scale; d = days; ECG = electrocardiogram; ET = early termination;

; IP = investigational product; M = Month; MoCA = Montreal Cognitive

Assessment:

SAE = serious adverse event;

[figure not shown]
UHDRS = Unified Huntington's Disease Rating Scale;

- ^a For 718-CIH-301 v2 Completers, the "Next Scheduled Study Treatment Visit" may be any visit within the Treatment Period and will depend on the participant's visit schedule, which will remain relative to the date of their Day 1 visit.
- ^b Participants who terminate the study early should complete an ET visit ([Table 8](#)) within 7 days of IP discontinuation and return to the clinic for a Safety Follow-Up Visit 30 days \pm 7 days after the ET visit.
- ^c Vital signs include body temperature, respiratory rate, heart rate, and blood pressure. On dosing days, vital signs will be measured prior to dosing. Blood pressure and heart rate will be measured after the participant has been in the supine position for at least 5 minutes and then repeated approximately 1 and 3 minutes after standing at all scheduled time points. Vital signs can be repeated once per visit if out of range.
- ^d Brief assessment of general appearance, cardiovascular, respiratory, gastrointestinal, and neurological systems, followed by a targeted physical assessment as needed. A symptom-directed examination may be conducted at any time at the discretion of the investigator.
- ^e A single ECG will be measured after the participant has been in the supine position for at least 5 minutes.
- ^f Safety laboratory assessments will include blood samples for hematology, biochemistry, coagulation, and urine samples for urinalysis. On dosing days, samples will be collected \leq 2 hours prior to dosing.
- ^g Only applicable for female participants that are not postmenopausal or surgically sterile. For scheduled clinic visits, urine pregnancy tests will be conducted. For remote visits (Months 27, 33, 39, and 45), start and end dates of the last menses will be collected.

- ^p Participants will bring all used packaging and unused IP to the clinic at each in-clinic visit for study staff to review and document.

- q Study staff will dispense sufficient IP for the participant to take daily at home until the next scheduled visit. IP will be shipped to the participant's home at remote visits (Months 27, 33, 39, and 45).
- r At scheduled clinic visits, participants will self-administer IP in the clinic under the supervision of study staff. All scheduled safety assessments will be conducted prior to dosing [REDACTED] will be administered post dosing.
- s At remote visits, site staff will check AiCure and query the participant about any missed doses or noncompliance.

Table 9:

APPENDIX B. HANDLING OF MISSING DATES

Dates missing the day, or both the day and month of the year will adhere to the following conventions in order to classify TEAEs and to classify prior and concomitant medications.

In general, listings will present the actual partial or missing values rather than the imputed values that may be used in derivation. In instances where imputed values will be presented, imputed values will be flagged.

Adverse Events

If the AE start date is completely missing, do not impute a date but consider it as TEAE, unless the AE end date is before the initiation of treatment, in which case the AE will be considered prior.

For partial AE start dates:

- When the year is known, but the month and day is unknown, then:
 - If the year matches the year of first dose date and the end date (if present) is after first dose date, or AE is ongoing, then impute as the month and day of the first dose date.
 - If the year of AE onset < year of initiation of the treatment, then the month and day will be set to December 31st.
 - If the year of AE onset > the year of initiation of treatment, then the month and day will be set to January 1st.
- If the year and month are known, but the day is unknown, then:
 - If the year of AE onset = the year of initiation of the treatment and:
 - the month of AE onset = the month of initiation of the treatment, then the day will be set to the day of initiation of the treatment.
 - the month of AE onset < the month of initiation of the treatment, then the day will be set to the last day of month.
 - if the month of AE onset > the month of initiation of the treatment, then the day will be set to the 1st day of month.
 - If the year of AE onset < the year of initiation of the treatment, then the day will be set to the last day of month.
 - If the year of AE onset > the year of initiation of the treatment, then the day will be set to the 1st day of month.

If the imputed AE onset date is after the AE stop date, then the onset date will be set to the stop date.

- When the year and day are present and the month is missing, treat it as if the day is missing, and only year is present. Follow the imputation rules for “year is known, but the month and day is unknown”.
- When the year is missing, but the month and/or day is known, treat this date as missing; do not impute.

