8.3.1. Adverse Events

An AE is any untoward medical occurrence in a patient or clinical investigation participant and that does not necessarily have a causal relationship with this treatment. An AE can therefore be any unfavorable and unintended sign (including an abnormal laboratory finding), symptom or disease temporally associated with the use of a medicinal (investigational) product whether or not related to the medicinal (investigational) product. In clinical studies, an AE can include an undesirable medical condition occurring at any time, including baseline or washout periods, even if no study treatment has been administered.

Adverse events will be coded using Medical Dictionary for Regulatory Activities (MedDRA) Version 25.1.

A TEAE is defined as an AE with onset on or after the first dose of SAGE-718- - either in the parent study or within this protocol and on or after the ICF sign off date. For more clarification, a TEAE is defined as below:

- For Placebo rollover participants from parent study: TEAE is defined as an AE with onset on or after the first dose of SAGE-718 in this protocol.

- For SAGE-718 rollover participants from the parent study: TEAE is defined as an AE with onset on or after the ICF sign off in this protocol.

Pre-treatment AE is defined as below.

- For Placebo rollover participants from parent study: Pre-treatment AE is defined as an AE with onset before the first dose of SAGE-718 in this protocol and after ICF sign off date in this protocol or ongoing AE from parent study.
- For SAGE-718 rollover participants from the parent study: Pre-treatment AE is defined as an AE with onset after ICF sign off date in this protocol and before the first dose date of IP in the current protocol.

On-treatment TEAE:

- For Placebo rollover participants from parent study: On-treatment TEAE is defined as an AE with onset on or after the first dose of SAGE-718 in this protocol and on or before IP last dose date + 30 days (Note that time does not matter for the end of this period. i.e. if AE occurred after the last dose but on the same date of last dose, it is considered as on-treatment TEAE).
- For SAGE-718 rollover participants from the parent study: On-treatment TEAE is defined as an AE with onset on or after first IP dose date/time and on or before IP last dose date + 30 days.

Post-treatment TEAE: AE onset date on or after IP last dose date + 31 days.

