^g Vital signs include body temperature, respiratory rate, heart rate, and blood pressure. On dosing days, vital signs will be measured prior to dosing. Blood pressure and heart rate will be measured after the participant has been in the supine position for at least 5 minutes and then repeated approximately 1 and 3 minutes after standing at all scheduled time points. Vital signs can be repeated once per visit if out of range.

- h The final physical and neurological examinations will be carried over from the parent study and will serve as Day 1 assessments in the current study. A full physical and neurological examination is to be conducted on Day 180. At other visits, physical examinations will include a brief assessment of general appearance, cardiovascular, respiratory, gastrointestinal, and neurological systems and followed by a targeted physical assessment as needed. A symptom-directed examination may be conducted at any time at the discretion of the investigator.
- i To include hepatitis B and C screening tests, HIV-1 and -2 antibody.
- j A single ECG will be measured after the participant has been in the supine position for at least 5 minutes.
- k Safety laboratory assessments will include blood samples for hematology, biochemistry, coagulation, and urine samples for urinalysis. On dosing days, samples will be collected \leq 2 hours prior to dosing.
- l Urine pregnancy tests will be conducted at scheduled time points for female participants that are not postmenopausal or surgically sterile.
- m [REDACTED]
- n [REDACTED]
- o Only applicable for direct rollover participants that did not provide sample(s) in the parent study.
- p [REDACTED]
- q [REDACTED]
- r [REDACTED]
- s [REDACTED]
- t [REDACTED]
- u [REDACTED]
- w At scheduled clinic visits, participants will self-administer IP in the clinic under the supervision of study staff. All scheduled safety assessments will be conducted prior to dosing. [REDACTED] will be administered post dosing. (All Day 1 assessments should be done predose).
- x Study staff will dispense sufficient IP for the participant to take daily at home until the next scheduled visit.
- y Participants will bring all used packaging and unused IP to the clinic at each visit for study staff to review and document.
- z AEs/SAEs will be collected beginning with completion of 718-CIH-301 informed consent through end of study participation. Documented ongoing AE/SAE from parent studies will be collected to follow through resolution.

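### SAP Appendix B has no exception for adverse events documented as ongoing from the parent study, so some with partial or missing onset dates would count as new TEAEs of study 301

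*SAP*

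**What the plan says.** SAP 6.1 states that Cohort 3 was not enrolled, so the analysis covers direct (Cohort 1) and gap (Cohort 2) rollovers only. Ongoing parent-study events are in the 301 data. For Cohort 1, SAP Appendix A, Table 6, footnote z reads: "Documented ongoing AE/SAE from parent studies will be collected to follow through resolution". Table 5, footnote z says the same for Cohort 2, and Protocol 13.6.1 agrees.

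SAP 8.3.1 defines a TEAE by onset:

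- **Placebo rollovers:** on or after the first SAGE-718 dose in 301. The pre-treatment class for this group explicitly adds "or ongoing AE from parent study".
- **SAGE-718 rollovers:** on or after 301 consent. The pre-treatment class covers only the interval from 301 consent to first dose and does not mention ongoing parent-study events.

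The same section presumes an event to be a TEAE when an incomplete date leaves its timing relative to dosing undetermined.

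Appendix B gives these rules for incomplete onset dates:

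- **Year only, same year as first dose:** the rule applies to an event that stopped later than first dose, and adds "or AE is ongoing, then impute as the month and day of the first dose date".
- **Year only, earlier year:** "If the year of AE onset < year of initiation of the treatment, then the month and day will be set to December 31st".
- **Year and month, same month as first dose:** "the month of AE onset = the month of initiation of the treatment, then the day will be set to the day of initiation".
- **Year and month, earlier month:** "the month of AE onset < the month of initiation of the treatment, then the day will be set to the last day" of that month.
- **Completely missing:** "do not impute a date but consider it as TEAE", unless the event ended before treatment.

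The imputed onset is capped at the event's own stop date. Nothing caps it at the end of the parent study or at 301 consent.

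**The concern.** An event recorded as ongoing from the parent study has a known position in time even when its onset date is incomplete: it began before 301. Appendix B does not use that information. Where the known part of the date matches the first-dose year or month, or where no date is recorded, the event is treated as if it might have begun on 301 treatment.

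The proportion of participants with TEAEs is the first primary endpoint (SAP 4.1). An event moved in this way would enter that count, the tables by system organ class and preferred term, and the severity and relationship tables. If dated to the 301 first dose, it would also be labelled an on-treatment TEAE. An event that arose in the parent study would be presented as new on open-label SAGE-718. The mechanism can only add TEAEs.

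**Working it through.** The plan states no figure on this point, so the check applies the rules to an example and then illustrates how often they bite.

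**1. The rules applied.** Take a first dose in 301 on 10 March 2023 and an event ongoing from the parent study and still ongoing.

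| Recorded onset | Onset after Appendix B | On or after first dose? |
|---|---|---|
| 2023 | 10 Mar 2023 | Yes: TEAE |
| Mar 2023 | 10 Mar 2023 | Yes: TEAE |
| Completely missing | none imputed | Taken as TEAE by rule |
| Feb 2023 | 28 Feb 2023 | No |
| Dec 2022 | 31 Dec 2022 | No |
| 2022 | 31 Dec 2022 | No |

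The comma before the ongoing clause permits a second parsing, in which every ongoing event with a year-only date takes the first-dose month and day. Only month and day are imputed, so the last row would become 10 March 2022, still before first dose. Both parsings move the same events to first dose or later.

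**2. Comparison with SAP 8.3.1.**

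- *Placebo rollovers.* The first three rows are TEAEs under Appendix B. The same events are pre-treatment under 8.3.1 because they were ongoing from the parent study. No text says which rule prevails.
- *SAGE-718 rollovers.* Without imputation the true onset precedes 301 consent, so the event meets neither the TEAE nor the pre-treatment definition. After imputation it meets the TEAE definition. The problem here is a missing class.
- *A narrower route.* For SAGE-718 rollovers in Cohort 2, a month-end imputed date can fall between 301 consent and first dose and so count as a TEAE. This is why earlier-month onsets are mostly, not always, unaffected.

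**3. How often a partial date would be moved.** Assumptions: first-dose dates uniform over a calendar year; onsets uniform over a parent study of 112 days (718-CIH-201) or 42 days (718-CIH-202), the final visit days in Protocol Table 3, footnote f. The gap runs from parent-study end to 301 first dose.

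| Gap | Year-only, 112 days | Year-only, 42 days | Year-month, 112 days | Year-month, 42 days |
|---|---|---|---|---|
| 0 days | 84.5% | 94.1% | 13.1% | 35.0% |
| 7 days | 82.6% | 92.2% | 7.7% | 20.6% |
| 30 days | 76.3% | 85.9% | 0% | 0% |
| 180 days | 35.2% | 44.8% | 0% | 0% |

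These are shares of carried-over ongoing events that already have that kind of partial date, not shares of all events.

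**4. Effect on the participant-level proportion.** The documents give neither the frequency of carried-over events nor that of partial dates. Assume 20% of participants have a carried-over ongoing event and 5–10% of those have a qualifying partial date:

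- 0.20 × 0.05 = 1%
- 0.20 × 0.10 = 2%

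With an assumed 150 participants, 150 × 0.20 × 0.05 = 1.5 and 150 × 0.20 × 0.10 = 3. These are upper figures for the assumed rates, because a participant with any other 301 TEAE is already counted.

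**The case against.** The strongest reply is that 8.3.1 already settles the matter. Its placebo-rollover class rests on status, not on date, and a specific status rule may reasonably govern over a generic date convention. The TEAE presumption in 8.3.1 also applies only when timing is undetermined, which is not so for a documented parent-study event. This is a sensible way to program it, but the SAP does not say so, Appendix B states that its purpose is to classify TEAEs, and the argument gives SAGE-718 rollovers no class.

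A second reply concerns the anchor. Appendix B does not say which study's first dose is meant. The 301 dose is the natural reading, since SAP 8.1 ties baseline to the first dose in the current study and 8.1.1 sets Study Day 1 at first dose. If the parent-study dose were meant for SAGE-718 rollovers, the imputed onset would precede 301 consent and would not be a TEAE. The placebo-rollover conflict would remain, because their first SAGE-718 dose is in 301.

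Other points limit the weight of the concern. Protocol 12.2.5 asks for onset date and time, so qualifying partial dates may be rare. The report is synoptic and descriptive, with no test or threshold. Listings generally show the actual partial dates, so a case could be seen. For Cohort 1, a short gap between parent-study end and 301 does not mean that the onset shares the first-dose month: for the 112-day study, expected to supply 128 of 156 rollovers, the illustration gives only 7.7–13.1% at gaps of 0–7 days. Cohort 1 is still the more exposed cohort, chiefly through year-only dates.

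**Conclusion.** The point holds in a limited form. Appendix B would turn some events documented as ongoing from the parent study into 301 TEAEs: those with a year-only onset in the first-dose year, those with a year-month onset in the first-dose month, and those with no onset date. For placebo rollovers this contradicts SAP 8.3.1; for SAGE-718 rollovers it fills a gap in 8.3.1 with the wrong answer. Except for completely missing dates, the conclusion rests on reading first dose as the 301 first dose.

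A reader might infer that every ongoing event with an incomplete date is moved to first dose, or that the SAP's own class is contradicted in both parent arms. The documents support neither: earlier-year and earlier-month onsets generally stay before first dose under either parsing, and only the placebo-rollover definition names ongoing parent-study events.

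The direction is certain (upward) and the size unknown. It is probably small: at most 1–2 percentage points on the assumed rates. This is a minor correction, worth making because it touches the first primary endpoint and is cheap.

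**What to change.** State in Appendix B that the first dose date means the first dose in 301, and add:

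*An AE recorded as ongoing from the parent study is not a TEAE by onset, whatever part of its onset date is missing; any imputed onset is capped at the day before 301 informed consent. It is classed as pre-treatment for placebo rollovers (as in 8.3.1) and listed as ongoing from the parent study for SAGE-718 rollovers. Worsening after the start of IP is handled under the protocol's TEAE definition.*

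That definition is in Protocol 12.2.1, so genuine worsening on treatment is still captured. Mirror the SAGE-718-rollover handling in 8.3.1 so that the two places agree. The existing rules continue to apply to all other events.

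The cost is a short SAP insertion and one programming condition on the carry-over record; no new data are needed. Counting carried-over events with partial or missing onset dates, by parent arm and cohort, would replace the assumed rates above with the actual size. If the database is already locked, SAP section 2 requires the change to be documented and discussed in the clinical study report.
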